If a clinically serious sign or symptom is reported the medical monitor will contact the sponsor and no further enrollment will be done until the medical monitor or sponsor gives permission. In the previously completed clinical study evaluating intracorporal administration of up to 16000 μg *hMaxi-K* in 20 participants with ED, there was only one adverse event considered possibly related to *hMaxi-K* ("tingling warmth in the glans").

To minimize the possibility of dehydration and/or a vasovagal response following injection of the *hMaxi-K*, participants will be instructed to eat breakfast and drink fluids on that morning.

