5.2.1 Dose Limiting Toxicity

A DLT is defined as the occurrence within the first 4 weeks following a single administration of *hMaxi-K* of an unacceptable toxicity, as described below. Adverse events for cardiovascular, blood chemistry, complete blood count, or urine categories of adverse events will be graded according to the criteria provided in [Appendix A](#).

No acute toxicity was seen in the preclinical studies with administered doses up to 1000 μg (approximately 1500 $\mu\text{g}/\text{kg}$) or in men and women given doses up to 16000 μg . Potential toxicities would be those that could occur due to enhanced efflux of K^+ with resultant decreased intracellular Ca^{++} concentration thus altering smooth muscle function in diverse organ systems.

The following criteria will be used to define:

DLT:

- 1) Any adverse events of Grade 2 or higher in the cardiovascular category of adverse event criteria listed in [Appendix A](#);
- 2) Any adverse events of Grade 2 or higher in the blood chemistry, complete blood count, or urine categories of adverse event criteria listed in [Appendix A](#).

- 3) Penile pain and/or erection that persists for more than four hours after gene transfer;
- 4) Change in random hormone levels greater than 2 times the upper or lower limits of normal at any time post dosing..

Stopping Rule

If within 4 weeks following the single administration of *h*Maxi-K, if any participant experiences a grade 3 or higher dose limiting toxicity, no additional participants will be accrued and no further doses of *h*Maxi-K (or placebo) will be administered. Clinical data regarding the event will be collected, reviewed, and discussed with the Ethics Committee (EC) and Kuwait Ministry of Health (MOH). After review of these data with EC and MOH the clinical study may resume only with concurrence of EC and MOH.

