9.4 Severity of Adverse Event

Adverse events included in the toxicity table ([Appendix A](#)) will be graded according to the definitions provided. For adverse events not listed in the toxicity table, assignment of grade based on intensity of symptoms, degree of limitation of usual daily activities, or level of abnormality of objective clinical signs or laboratory parameters will be according to severity using the following criteria:

- Grade 1: transient or minimal symptoms; not interfering in function or ability to perform activity of daily living or require a medication change. No medical intervention required.
- Grade 2: symptoms interfering in function but not with activities of daily living. Minimal or no medical intervention required.
- Grade 3: incapacitating symptoms that interfere with function and activities of daily

living; required bed rest and/or resulted in loss of work or cancellation of social activities. Medical intervention required. Hospitalization possible.

- Grade 4: Considered potentially life threatening (see definition under section 9.2)

A serious adverse event (SAE) requires medical intervention to prevent permanent impairment or death, permanently disability: (bed-ridden or disabling AE), required significant medical intervention/therapy, hospitalization or hospice care or in the judgment of the investigator was a medically significant event. Serious adverse events may be mild, moderate or severe in intensity (e.g., mild stroke).

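### An erection lasting over four hours is a DLT with no grade of its own: it can be graded 2 and miss the Stopping Rule, and no scheduled contact falls near the four-hour mark

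*Protocol*

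**What the plan says.** Protocol 5.2.1 lists four DLT criteria. Criteria 1 and 2 are Appendix A events of Grade 2 or higher. Criterion 3 is "Penile pain and/or erection that persists for more than four hours after gene transfer". Criterion 4 is a hormone change measured against the normal limits. Criteria 3 and 4 carry no grade.

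The Stopping Rule in the same section applies if, within four weeks of the injection, any participant "experiences a grade 3 or higher dose limiting toxicity, no additional participants will be accrued"; dosing stops as well. On restart it says: "After review of these data with EC and MOH the clinical study may resume only with concurrence of EC and MOH".

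Appendix A grades hematology, chemistry, urinalysis and cardiovascular events only. For everything else, section 9.4 says: "For adverse events not listed in the toxicity table, assignment of grade based on intensity of symptoms, degree of limitation of usual daily activities", or on the level of objective abnormality. Grade 2 reads "symptoms interfering in function but not with activities of daily living. Minimal or no medical intervention required". Grade 3 calls for incapacitating symptoms and medical intervention.

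Two other provisions bear on the event. Section 9.5 requires events meeting the four criteria to reach the sponsor within 24 hours. Section 5.2 adds a hold when a sign or symptom is clinically serious, a term left undefined: "no further enrollment will be done until the medical monitor or sponsor gives permission".

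On detection, section 7.2 keeps the participant in the clinic for two hours after injection. In that time the penis is inspected for a persistent erection and he is asked about pain. Appendix B places the next visit, Visit 3, at week 1 with a window of two days either side.

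**The concern.** Criterion 3 is defined by how long the event lasts. The stop is decided by how severe it is, on a scale where duration does not appear. The protocol therefore names an erection over four hours as an unacceptable toxicity without fixing what follows from it.

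The grade also decides who controls restart. At Grade 3, dosing stops and two outside bodies must agree before it resumes. At Grade 2, the most that section 5.2 provides is a hold on enrollment that the medical monitor or sponsor can lift. Two careful investigators could grade the same episode differently and so send the trial down different routes.

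The product is meant to relax the smooth muscle of the corpora, and the sponsor itself chose four hours as the limit. Yet scheduled observation ends before that limit can be reached.

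**Working it through.** The plan states no figure on this point, so the main check sets the sections side by side.

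**Path of a criterion 3 erection**
1. It lasts more than four hours, so it is a DLT (5.2.1).
2. Appendix A has no row for erection or penile pain, so it yields no grade.
3. Section 9.4 then applies, using symptoms, activity limits, intervention and objective findings.
4. If it is treated, the Grade 3 wording on intervention fits, and the Stopping Rule probably fires.
5. If it resolves with minimal or no intervention and daily activities are unaffected, the Grade 2 wording fits. It is a DLT and the Stopping Rule does not fire.

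Grade 2 is therefore attainable.

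**Detection gap**
- Inputs: observation of 2 h (7.2); criterion of 4 h (5.2.1); Visit 3 at day 7 ± 2, which is day 5 to day 9 (Appendix B).
- Shortest gap after observation ends: 5 × 24 − 2 = 118 h.
- Longest gap: 9 × 24 − 2 = 214 h.

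Between these points detection relies on the section 9.5 instruction that participants report new symptoms.

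**What the earlier study can exclude**
Section 5.2 says that, "in 20 participants with ED, there was only one adverse event considered possibly related to" the product, and that event was not an erection. I read this as 0 related prolonged erections in 20 men. The exact one-sided 95% upper bound is 1 − 0.05^(1/20) = 0.139, or 13.9%. Doses in that study ran up to 16000 µg and the split is not given, so this is not a bound for either arm here.

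**Illustration under assumed rates**
The true rate p of erections over four hours is not in the documents. With 11 + 11 = 22 men on active drug, the chance of at least one is 1 − (1 − p)^22:

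| Assumed p | Chance of at least one in 22 |
|---|---|
| 0.5% | 10.4% |
| 1% | 19.8% |
| 2% | 35.9% |
| 5% | 67.6% |

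These figures cover any erection over four hours, whatever its grade. They are upper limits on the chance that the proposed sentence adds a pause because of men on active drug. They do not measure the grading gap, which concerns only episodes graded below 3.

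**The case against.** The strongest reply is that nothing is missing. Section 9.4 grades every event that Appendix A omits, and a DLT tier below the stop is how the whole rule is built: a Grade 2 cardiovascular event is also a DLT that does not halt the trial. On this view an erection that resolves untreated and limits nothing is the mildest form, and review by the sponsor is enough. It would be reported within 24 hours. An important medical event that may require intervention can also be reported as serious under section 9.2. An erection starting at injection would be seen at the two-hour inspection.

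Much of this stands. Two tiers are a coherent choice, and the event would not go unmonitored once known. What remains is that for criteria 1 and 2 both tiers are anchored in Appendix A, while for criterion 3 the scale ignores the feature that defines the event. If some erections over four hours are meant not to stop dosing, the protocol does not say which. The inspection cannot establish a four-hour duration.

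Four stronger readings are tempting, and the documents do not support them:
- **Sections 5.2.1 and 9.5 conflict on halting.** Section 9.5 places the four criteria under the Stopping Rules, but it requires only that the sponsor be told. The label is loose; it does not order a second kind of halt.
- **The event could be Grade 1.** That grade does say "No medical intervention required", but it also expects brief or slight symptoms with no effect on function. An erection over four hours fits that poorly.
- **Prolonged erection is the main local risk.** No section ranks it so. Section 5.2.1 speaks of smooth muscle in diverse organ systems, and section 1.4 has the added channels acting on a normal erectile stimulus, so risk is not shown to concentrate in the first hours.
- **The 10% to 68% range is the size of the problem.** It rests on assumed rates of any such erection.

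**Conclusion.** The point holds in a limited form. An erection over four hours can be a DLT graded 2, below the Grade 3 stop, because its grade comes from a scale that does not use duration. A treated episode would probably stop the trial as written. For an untreated one that does not limit daily activities, the 24-hour report applies and the enrollment hold may apply, but EC and MOH agreement to restart is not required.

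Separately, no scheduled contact can promptly establish the criterion: observation ends at 2 hours against a limit of 4, and the next contact is 118 to 214 hours later.

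The conclusion on grading rests on the wording alone. The share of such erections that would be graded below 3 is unknown, and I do not estimate it. The earlier study is reassuring but, with 20 men, cannot exclude the risk. This is an inexpensive safety improvement, best made before a first event forces the question.

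**What to change.** 1. In Protocol 7.2, add a telephone contact 4 to 6 hours after injection, asking about persistent erection and pain.
2. In the Stopping Rule of 5.2.1, add: *An erection lasting more than four hours after gene transfer counts as a Grade 3 DLT.*

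Penile pain over four hours and the hormone criterion can stay under section 9.4, still able to stop the trial at Grade 3. Pain can be graded on intensity and limitation, which that scale does use.

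The cost is one call per participant (35 planned, about 40 with the attrition allowance), one added sentence, and a possible extra pause for EC and MOH review, including for an episode that proves benign. Clinic visits and sample size do not change. The call covers only the first hours, so later erections would still depend on self-report.

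Renaming the four items in section 9.5 as DLT criteria would be tidy, but it is editorial and the point does not depend on it.

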5.3 Concomitant Medications/Therapies

Participants will continue any medications they are receiving at study entry for underlying medical conditions with the exception of those described below. All medications taken by participants within two weeks of study entry (including over-the-counter preparations) will be recorded on the Medical History Form. Any changes in concomitant medication, including additions, discontinuations, and dose changes, occurring during the study will be recorded on the concomitant medication form.

Participants are not allowed to concomitantly use any approved, unapproved, or investigational medications or therapies intended to treat erectile dysfunction. These medications/therapies include, but are not exclusively: Viagra™, Cialis™, Levitra™, Muse™, prostaglandin E1 as Caverject™ or Edex™, Trimix, yohimbine, apomorphine (Uprima™), vacuum erection devices, or penile prosthetic implants.

6.0 Outcome Assessments and Procedures

6.1 International Index of Erectile Function (IIEF)

The International Index of Erectile Function (IIEF) ³⁵ is a validated, self-administered questionnaire that has been shown to be a cross-culturally and psychometrically valid measure of male erectile dysfunction.

The test contains 15 questions in five domains: (a) erectile duration (six items); (b) orgasmic function (two items); (c) sexual desire (two items); (d) intercourse satisfaction (three items); and overall sexual satisfaction (two items). The questionnaire has been accepted by the FDA and peer-reviewed scientific journals and is used currently as the clinical endpoint in all pivotal studies evaluating new drugs for erectile function.

The erectile function domain, questions 1-5, and 15 of the IIEF has been validated to assess erectile changes only. ^{36, 37} The EF domain of the IIEF will be completed at Visit 1 and V2-V7.

6.2 Sexual encounter profile (SEP)

The SEP is a questionnaire composed of 5 questions assessing sexual function. SEP 2 evaluates the penetrability of the erection and SEP 3 the maintenance of the erection. This questionnaire will be completed at V2-V7. See [Appendix C](#).

6.3 Physical Examination

6.3.1 Physical Examination

A complete physical examination, including a complete urogenital exam (see below), and review

of body systems will be performed at all visits. Vital signs (heart rate and blood pressure) and an examination of the penis (see below) will be performed at all visits. Height will be obtained at Screening only. Weight and oral temperature will be obtained at Screening and V7. Any untoward clinically significant change from Screening will be recorded on the CRF as an adverse event.

6.3.2 Physical Examination of the Penis

Physical examination of the penis will be done at each visit and will include inspection, and palpation.

6.4 Electrocardiograms

A 12-lead ECG will be performed at all visits: Screening (V1) Baseline (V2 -prior to treatment and at 1 and 2 hours post treatment), V3, V4, V5, V6, and V7. These ECGs obtained at the study centers, will be forwarded to a central reader for final interpretation. The over reader will return the results to the study center within 48 hours. This does not negate the responsibility of the staffconducting the study to initially review the ECG and to take appropriate clinical actions. The following parameters will be assessed: heart rate, rhythm, PR interval, QT interval, QTcF, QTcB, QRS duration, and overall evaluation.

6.5 Vital Signs

Vital signs will be performed at all visits. Vital signs should include an apical heart rate and brachial blood pressure (BP) both taken after 5 minutes resting in the sitting position (standard sphygmomanometry). Any clinically significant changes from screening will be recorded on the CRF as an adverse event. Following administration of study drug at V2, BP and heart rate will be measured and recorded every 15 minutes for 2 hours.

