7.1 Visit 1 (Study Week (-) 2 - Screening)

The following evaluations and tests will be performed:

- Preliminary Screening:
 - Obtain written informed consent process for study participant ;
 - Medical history including history of erectile dysfunction to assess eligibility for study treatment;
 - Physical examination including physical examination of penis;
 - Vital signs (BP, heart rate, oral temperature, weight and height)
 - Participant completes the IIEF (screening)
 - Complete screening if entry criteria are met on preliminary screening;
 - Obtain urine for routine urine analysis: microscopic RBC and WBC, protein, glucose, nitrites and specific gravity;
 - Electrocardiogram;
 - Fasting blood specimens for the following laboratory determinations:
 - Hematology: Complete Blood Count (CBC) with differential, platelet count, Partial Thromboplastin (PTT), Prothrombin Time (PT), sedimentation rate (sed rate), C-reactive protein (CRP).
 - Chemistry: Blood Urea Nitrogen (BUN), creatinine, electrolytes (Na⁺, K⁺, Mg⁺⁺, Ca⁺⁺, CO₂, Cl), albumin, alkaline phosphatase, ALT, AST, LDH, GGT, total bilirubin, total protein, glucose;
 - Hemoglobin A1c (diabetic participants);

- Endocrine: total testosterone, random cortisol, TSH, T4
- Schedule next study visit when screening laboratory results are available.

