7.2 Visit 2 (Study Week 0 - Administration of study drug)

Based on the participant fulfilling all eligibility criteria following the screening procedures (Visit 1), the participant will be considered eligible to receive study drug. If a participant is unable to receive test material because a clinically significant condition has evolved which, in the investigator's opinion, represents a potential safety risk the patient will be considered a screen failure.

The following tests and evaluations will be performed on eligible participants:

- Adverse events since screening visit;
- Physical examination including examination of the penis for changes since the screening visit;
- Vital signs (BP, heart rate);
- ECG prior to administration of study drug and at 1 and 2 hours post study drug;
- Participant completes SEP and IIEF Urine analysis: microscopic RBC and WBC, protein, glucose, nitrites and specific gravity;
- Plasma specimens will be collected to assay for the presence of *hSlo* DNA by PCR. These will be kept frozen at -20° C or less at the site for eventual assay by Sponsor. Samples will be collected pre-dosing and at 2 hours post dosing.
- Administer study drug. The participant will be observed in the clinic for two hours after the injection. During that time blood pressure and heart rate will be measured and recorded by the nurse every 15 minutes. ECG will be done at one and two hours after administration of study drug and reviewed by a physician at those times. The penis will be inspected for ecchymosis or persistent erection. The participant will be asked if there is any persistent pain at the injection site and will be treated symptomatically, if needed. The participant will be asked if symptoms of malaise, vertigo, light-headedness, and nausea are present. Emergency equipment for resuscitation will be immediately available in the event of an unexpected serious reaction to the study drug.

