9.0 Adverse Events Definitions and Monitoring

9.1 Adverse Event

An adverse event is any unfavorable and unintended diagnosis, symptom, sign (including an abnormal laboratory finding), syndrome or disease which either occurs during the study, having been absent at baseline, or, if present at baseline, appears to worsen.

A treatment emergent adverse event (TEAE) will be considered an event that is temporally associated with the use of the study drug, whether or not considered related to the study drug.

Examples of AEs are as follows:

- Changes in the general condition of the participant
- Subjective symptoms offered by or elicited from the participant
- Objective signs observed by the Investigator or other study personnel
- All concurrent diseases that occur after the start of the study, including any change in severity or frequency of preexisting disease
- All clinically relevant abnormalities in laboratory values or clinically relevant physical findings that occur during the study.

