## STATISTICAL ANALYSIS PLAN

### ION04ED

#### Schedule of Events

Test or Procedure	Visit 1 -2 Week Screening	Visit 2 Week 0	Visit 3 Week 1 ± 2 days	Visit 4 Week 4 ± 3 days	Visit 5 Week 8 ± 3 days	Visit 6 Week 12 ± 3 days	Visit 7 Week 24 ± 3 days
Informed Consent Process	X						
Medical History	X	X 	X	X	X	X	X
Physical Examination	X	X 	X	X	X	X	X
Physical Examination of Penis 	X	X 	X	X	X	X	X
Blood Tests (Chemistry and Hematology) 	X 		X	X		X	X
Urine analysis 	X	X 	X	X		X	X
ECG 	X	X 	X	X	X	X	X
IIEF 	X	X 	X	X	X	X	X
SEP 		X 	X	X	X	X	X
Study drug administration		X					
Assay for h Slo DNA 	X 	X	X	X	X	X	X

PE of penis includes: inspection, palpation and neurosensory testing

Blood tests include: Hematology (CBC with differential, platelet count, PTT, PT, sedimentation rate, CRP), Chemistry (BUN, Cr, Na+, K+, Mg++, Ca++, CO2, Cl, albumin, alkaline phosphatase, ALT, AST, total bilirubin, total protein; Endocrine (testosterone, random cortisol, TSH, T4). Hemoglobin A1c and prolactin at Screening (V1) only.

Urine analysis includes: microscopic RBC and WBC, protein, glucose, and specific gravity.

ECG at V2 will be done prior to administration of study drug and at 1 and 2 hours following administration of study drug

Test will be done prior to administration of study drug.

In all participants, plasma specimens will be collected to assay for the presence of *h*Slo DNA by PCR. At Visit 2 collect pre- dosing and 2 post dosing.

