## 6. Definition

- **Age:** The age will be calculated as the exact number of days between the date of birth and date of informed consent converted to years (i.e. difference in days/365.25). Age is the integer part of this value.
- **Baseline:** The time point at which randomization is performed will be the baseline time point. The last instance of data collected before administration of treatment will be considered as the baseline information for the respective parameter. If a patient has repeated assessments prior to the start of double-blind study drug, then the results from the final assessment made prior to the start of double-blind study drug will be used as baseline.
- **Body Mass Index (BMI):** BMI is obtained by dividing the weight (kg) by the square of height (m) i.e. weight (kg)/ height (m).
- **Change between baseline and post dose visits** for the parameters will be considered as the difference between the post baseline value and the baseline value (post baseline value – baseline value). This will be applicable to laboratory data and safety parameters.
- **Prior/ Concomitant Medication/Therapy:** All medications/therapies with end date prior to the date of treatment will be considered as prior medications. Concomitant medication will be defined as any medication taken between the day of dosing with study drug and the end of the 6 month study follow-up period (or final visit). Any medications started after the final visit will not be considered concomitant medications.
- **Treatment Emergent Adverse Events (TEAEs):** A treatment emergent adverse event (TEAE) will be considered as an event that is temporally associated with the use of the study drug, whether or not considered related to the study drug. All adverse events with start date on or after the date of treatment will be considered as TEAEs.

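### Examination and vital-sign adverse events are judged against Screening rather than the pre-dose baseline, and the SAP's date-only TEAE rule counts findings made before injection on the dosing day

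*Protocol*

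**What the plan says.** For vital signs, Protocol 6.5 tells the site: "Any clinically significant changes from screening will be recorded on the CRF as an adverse event". Protocol 6.3.1 has the matching rule for the physical examination: "Any untoward clinically significant change from Screening will be recorded on the CRF as an adverse event". Screening is Visit 1, at Week -2 (Protocol 7.1). The injection is given at Visit 2, Week 0 (Protocol 7.2).

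At Visit 2 the site asks about "Adverse events since screening visit" and carries out an examination, listed as "Physical examination including examination of the penis for changes since the screening visit". Protocol Appendix B attaches footnote 5 ("Test will be done prior to administration of study drug", worded the same in the SAP's copy of the schedule) to the Visit 2 general and penile examinations, but not to the Visit 2 vital signs. Only the order of the list in 7.2 implies that blood pressure and heart rate are taken before the injection. After it, 6.5 requires both at 15-minute intervals over two hours.

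Two other places use a different reference. Under Protocol 9.1 an adverse event is one that occurs during the study, "having been absent at baseline, or, if present at baseline, appears to worsen". SAP section 6 then fixes the meaning of baseline: "The last instance of data collected before administration of treatment will be considered as the baseline information for the respective parameter".

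SAP section 6 also makes an event treatment-emergent if its start date is the treatment date or later; time of day plays no part. Protocol Appendix A grades hypertension partly by a diastolic rise of more than 20 mmHg, and haemoglobin partly by the size of a fall, without naming the visit from which the change is measured.

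**The concern.** The same reading can be an adverse event under one section and not under another. A site following 6.5 compares a reading taken minutes after injection with one taken two weeks earlier, while the SAP's tables compare it with the last pre-dose value. The adverse-event listing and the change-from-baseline table can then disagree about the same man.

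The date-only TEAE rule adds a second problem. The Visit 2 examination is meant to find changes since Screening before the man is injected. If it finds one and the onset is entered as that day, the SAP counts it as treatment-emergent although it came before the treatment.

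Safety is the primary objective in Protocol section 2.0, and the SAP summarises TEAEs in detail. In arms of 11, 11 and 13, single events matter. Grade 2 or higher cardiovascular events also count as dose-limiting toxicities (Protocol 5.2.1), so an unstated reference for change-based grades can affect how an individual case is graded.

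**Working it through.** The plan gives no figure on this point to reproduce. The check is a comparison of the passages, followed by arithmetic on what one event is worth.

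**Step 1. The references side by side.**

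| Place | Reference |
|---|---|
| Protocol 6.3.1, 6.5 | Screening, Week -2 |
| Protocol 7.2, Visit 2 examination | Screening (a pre-dose check) |
| Protocol 9.1 | Baseline, not defined there |
| Protocol 6.4, 6.6 | Visit 2 pre-dose ECG and plasma sample called baseline |
| SAP 6 and 9.4 | Last value before treatment |
| Protocol Appendix A, change-based grades | Not stated |

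**Step 2. Follow a change through the rules.**

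- It arises between Visits 1 and 2 and is dated before the dosing day. The Visit 2 inquiry and Protocol 9.5 capture it, and the SAP rule leaves it out of the TEAEs. This is handled correctly.
- It is first found at the Visit 2 pre-dose examination and dated that day. Its start date equals the treatment date, so it is a TEAE. This is wrong.
- A reading is taken after injection. Its AE status depends on whether the site applies 6.5 or 9.1.

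**Step 3. Both directions of disagreement, with hypothetical diastolic values (mmHg) and the Appendix A mark of more than 20.**

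- Screening 75, pre-dose 90, post-dose 97: 97 − 75 = +22 against Screening, but 97 − 90 = +7 against pre-dose.
- Screening 90, pre-dose 75, post-dose 97: 97 − 90 = +7 against Screening, but 97 − 75 = +22 against pre-dose.

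**Step 4. What one event is worth.** 1/11 = 9.1 percentage points and 1/13 = 7.7 percentage points.

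**Step 5. Illustration only.** Assume a between-day diastolic SD D of 4 to 8 mmHg, a within-day reading SD e of 3 to 5 mmHg, 120/15 = 8 post-dose readings, and an automatic flag at more than 20 mmHg. None of the SDs is in the documents. The simulation used 400,000 draws per setting.

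| Quantity | Against Screening | Against pre-dose |
|---|---|---|
| No drug effect: at least one of 8 readings flagged | 0.9% to 15.6% | 0.0% to 1.5% |
| Pre-dose reading itself already flagged | 0.2% to 6.7% | not applicable |
| True rise of 25, one reading: not flagged | 24% to 35% | 12% to 24% |

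Closed-form check: the pre-dose minus Screening difference has variance 2(D² + e²). For D = 4, e = 3 the SD is √50 = 7.07, 20/7.07 = 2.83, and the upper tail is 0.2%. For D = 8, e = 5 the SD is √178 = 13.34, 20/13.34 = 1.50, and the upper tail is 6.7%. Both agree with the table.

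The rates depend heavily on the rule. With the largest of eight readings and SD pairs (D, e) of (5,3), (6,4) and (8,4), a true rise of 25 is missed in 12% to 19% against Screening and in about 1% or less against pre-dose. In this model the pre-dose reference helps only on the dosing day; at later visits the two references are equally noisy.

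**The case against.** The best reply is that this is a wording inconsistency with safeguards around it. Much of that stands, and it rules out several stronger readings.

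- *A reader might infer that real acute changes go unseen.* The documents do not support this. Section 6.5 says that changes from Screening are recorded, not that only those are. Protocol 9.1 makes a worsening from baseline an adverse event, and 9.5 requires all observed events to be recorded. The readings are kept: SAP 9.2 summarises vital signs at each time point at which they are collected, and SAP 9.4 reports change from baseline at post-dose visits.
- *A reader might infer that any change between Visits 1 and 2 is counted as post-dose.* Only one dated to the dosing day is. Earlier onsets are asked about at Visit 2 and excluded by date. Nor is such a change a new event at every later visit, because SAP 9.4 counts a man once per preferred term.
- *A reader might infer bias towards one arm.* Differences between Screening and pre-dose values arise before treatment, and treatment is randomised and blinded, so no systematic difference between arms is expected.
- *A reader might take the simulated rates as estimates.* Section 6.5 turns on clinical significance, which is the investigator's judgement. The simulation replaces that with an automatic 20 mmHg flag and assumed SDs.
- *A reader might infer that the flagged rises would halt the trial.* An asymptomatic rise lasting under 24 hours is Grade 1 in Appendix A. The dose-limiting definition starts at Grade 2 and the stopping rule at Grade 3.

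Two things remain: the sections name different references, and the date rule cannot separate the hours before the injection from those after it.

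**Conclusion.** The point holds as an inconsistency with one definite consequence and one possible one. Definite: a finding made before the injection on the dosing day, and dated that day, is tabulated as treatment-emergent. Possible: a post-dose reading is judged for AE status against a two-week-old value, in either direction, if the site applies 6.3.1 or 6.5 rather than 9.1.

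The harm is noise in the AE and TEAE counts, at about 8 to 9 percentage points per event in one arm. How many events are affected cannot be derived from the documents. The conclusion rests on three assumptions: sites follow 6.3.1 and 6.5 as written; onset is recorded by date (Protocol 9.5 asks for a date, and the CRF is not among the documents); and Visit 2 vital signs are taken before injection, as the list order in 7.2 implies. The last is also what keeps the SAP's change-from-baseline summaries sound.

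**What to change.** 1. In Protocol 6.3.1 and 6.5, judge post-dose findings against the last available pre-dose value: Visit 2 where it was measured there, otherwise Screening. Keep Screening as the reference only for the Visit 2 pre-dose check. Simply replacing Screening with Visit 2 would fail, because weight and oral temperature are taken only at Screening and Visit 7, and the Visit 2 examination itself looks for changes since Screening. State in 9.1 that baseline has the SAP section 6 meaning.
2. In Appendix B, add footnote 5 to the Visit 2 vital signs.
3. On the CRF, record whether each dosing-day adverse event began before or after the injection. Change the SAP TEAE rule to onset or worsening after injection.
4. State the same reference for the change-based grades in Appendix A. Blood counts are not drawn at Visit 2, so for haemoglobin it remains Screening. No threshold changes.

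The cost is one extra CRF field and minor wording in the protocol and SAP. No new measurement is needed.
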